### **3.0 Intervention to be studied**

#### **Overview**

This study will perform the following research-specific procedures:

- 1) transcranial direct current stimulation (tDCS), the effect of which will be measured using
- 2) subdural electrocorticography (sECoG)

#### **Definitions and nomenclature**

tDCS **stimulation** as implemented in this protocol will be carried out through use of an array of five independently arranged electrodes (see Figure 1). sECoG **recording** will be carried out through use of an array of six electrode contacts arranged in a linear strip. The tDCS electrodes are separate devices placed on the scalp, while the sECoG contacts are encased in a single piece of silastic material, i.e., the sECoG electrode. Throughout the rest of this document, the tDCS electrodes and sECoG electrode will be referred to in the plural and singular forms, respectively. The terms 'electrode array' and 'electrodes' will be used interchangeably. Positioning the tDCS electrodes onto the scalp will be referred to as 'placement' of the electrodes, while positioning of the sECoG electrode inside the skull (but on top of the brain surface) will be referred to as 'insertion' of the electrode.

It is important to note that neither the tDCS nor sECoG electrodes will penetrate the brain at any time. Both electrodes will remain outside the brain itself. The tDCS electrodes will remain on top of the scalp; the sECoG electrode will remain underneath the skull and on top of the brain surface (see Figure 1, Step 3). Only the DBS electrode performed for standard of care treatment will penetrate the brain.

#### **Procedure steps**

In brief, standard of care DBS surgery involves drilling a 1.4 cm burr hole in the skull and implanting an electrode that penetrates the brain parenchyma into the basal ganglia or thalamus. For patients participating in this research, all surgical procedures will be the same, with the exception of the research-dedicated steps: 1) the sECoG electrode will be inserted using the same burr hole drilled previously but will remain on the surface of the brain and will not penetrate the brain, 2) the tDCS electrodes will be applied to the scalp (awake patients with frameless DBS will also be outfitted with virtual reality goggles), 3) the tDCS electrodes will be activated (awake, frameless DBS patients will perform up to two motor tasks before, during and/or after stimulation and videotaped during the task); the task will not be performed if the patient is awake but has a stereotactic headframe on or is asleep under general anesthesia, 4) in all patients the surgical site will be photographed to capture the tDCS montage as well as any other aspect of the setup relevant to offline reconstruction of behavioral and physiology data), 5)

all research-related equipment will be removed from the surgical field, 6) the subject will proceed to have the DBS surgery as per standard of care.

DBS surgery is reimbursed by insurers using a Diagnosis Related Group (DRG) model. This means that once a patient is preauthorized by an insurer to undergo DBS surgery, the surgery, hospital stay and all related procedures are bundled together and covered at a fixed cost. Costs related to research activity during this study (20 minutes total) will be charged to a research account and will not result in additional charges to the patient, hospital or the patient's insurer. In a recently published study documenting 200 cases of sECoG insertion during DBS surgery in movement disorder patients and in which all study related procedures took place in 20 minutes or less ('Intraoperative electrocorticography for physiological research in movement disorders: principles and experience in 200 cases', by Panov et al, 2017), **no infections related to the sECoG electrode occurred**. In this study, we will allow 20 minutes total to include setup and breakdown of the study-related equipment.

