In our previous study (Rowland et al, 2015), PD patients undergoing DBS surgery performed an arm-reaching task during subdural electrocorticography (sECOG) recording of beta (13-30 Hz) and broadband gamma (70-200 Hz) oscillations, showing modulation related to both movement preparation and execution. However, the exact frequency bands and phases of movement modulated by tDCS remain poorly understood. Patients undergoing DBS surgery for PD and ET are usually awake and, furthermore, the procedure provides access to primary motor cortex. Thus, during awake, frameless DBS surgery, responses in motor cortex can be measured safely in behaving subjects. Patients undergoing DBS surgery for dystonia are usually asleep, offering an opportunity to compare how tDCS affects motor cortical oscillations when patients are not engaged in a motor task. In some instances, PD and/or ET patients also request to be asleep during DBS surgery, allowing comparison between awake and asleep populations.

We will investigate the effect of tDCS on motor cortical oscillations in patients undergoing DBS surgery through the following specific aims:

**Aim 1. Quantify the change in primary motor cortical (PriMC) oscillations during cued arm reaching in relation to tDCS activation.** Question: Does tDCS differentially modulate movement preparation vs movement execution? In this aim, we will record beta and broadband gamma oscillations in PriMC in awake patients undergoing frameless DBS surgery using an

sECoG electrode while applying high-density tDCS focused on PriMC. Patients will be videotaped in order to correlate movement dynamics with ECoG signals. *We hypothesize that cortical beta and broadband gamma spectral power changes will be enhanced more so during movement preparation than execution following anodal tDCS activation.*

**Aim 2. Quantify the change in PriMC oscillations during framed DBS (either awake or under general anesthesia) in relation to tDCS activation.** Question: Does tDCS modulate motor cortical oscillations in the absence of movement? In patients undergoing framed DBS (either awake or asleep), cortical oscillatory changes will be recorded during application of tDCS using different amplitudes, durations, polarities, lateralities, and stimulation patterns. *We hypothesize that cortical beta and broadband gamma spectral power will be modulated using different amplitudes, durations, polarities, lateralities, and stimulation patterns in the absence of movement.*

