times. If no virtual touch is made at a location for 2 seconds, the blue dot will cycle to the next location automatically. Once the blue dot has cycled 5 times, both the blue and green dots will disappear and the red dot will reappear in the center of the screen (accompanied by an auditory cue) to complete 1 trial. Patients will be instructed to rest quietly when the red dot appears (rest phase). Appearance of the blue dot will signal that the patient is to prepare to move once the green dot appears (movement preparation phase). Patients will be instructed to move at a natural speed. This is to avoid confounding changes in beta and broadband gamma oscillations due to movement speed and force. Patients will be given an introduction to the task and an opportunity to practice several trials in the preoperative area while waiting for surgery to begin. Rest, movement preparation and movement execution will be analyzed as separate epochs. Beta and broadband gamma spectral power during each movement phase (rest, prep and move) will be analyzed separately. In our previous work (Rowland et al, 2015), the entire task took 3 minutes to complete. The entire task will be videotaped and repeated no more than twice. Videotaping will occur using a high-resolution web camera secured to a computer monitor facing the patient. The video signal is contemporaneous with all other data streams. Patients who are asleep will not perform the task or be videotaped.

All patients – whether awake or asleep – will undergo photography of the surgical site as well as any other aspect of the research necessary to reconstruct the electrode configurations (all patients) and/or behavioral task (awake, frameless DBS patients only).

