### **Behavioral task**

The primary risk from performing intraoperative behavioral tasks is fatigue. Patients will be asked to perform the reach-and-point motor task no more than twice. Patients will be asked during the interval if they need further rest and will be granted time (1 minute) to do so upon their request. Report of further fatigue will trigger immediate removal of the VR headset and electrodes, withdrawal of the patient from the study, and continuation with the DBS procedure.

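### Aim 1 asks for a change following tDCS, but the plan neither requires a task run before stimulation nor fixes a common run schedule

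*Combined protocol and SAP*

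**What the plan says.** Section 1.0 sets Aim 1 as "Quantify the change in primary motor cortical (PriMC) oscillations during cued arm reaching in relation to tDCS activation". Its hypothesis is that "cortical beta and broadband gamma spectral power changes will be enhanced more so during movement preparation than execution following anodal tDCS activation". The target is therefore a change, it is located after stimulation, and it is compared between two movement phases.

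One sentence places the task relative to stimulation. It is in Section 3.0, Procedure steps: "awake, frameless DBS patients will perform up to two motor tasks before, during and/or after stimulation and videotaped during the task". Section 9.0, Step 3, describes the task in detail but does not say when the current is on. It treats rest, preparation and execution as epochs to be analysed separately.

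The number of runs is given in three places. Section 3.0 has up to two. Section 9.0, Step 3, has "The entire task will be videotaped and repeated no more than twice". Section 13.0, Behavioral task, has "Patients will be asked to perform the reach-and-point motor task no more than twice".

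On time, Step 3 reports that in the group's previous study "the entire task took 3 minutes to complete", and Section 3.0 states that "we will allow 20 minutes total to include setup and breakdown of the study-related equipment".

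The design contains no sham condition, no unstimulated control and no randomised order. Sham control is mentioned only for outside trials, in Section 2.0 and in one reference title.

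**The concern.** A change needs a reference state measured on the same task. As written, a subject whose runs fall during and after stimulation, or who does a single stimulated run, has followed the protocol and contributes nothing to a paired before/after comparison. Subjects with before/during runs and subjects with before/after runs estimate different quantities, and only the second matches a hypothesis about what follows stimulation. Pooling them would give an average with no clear meaning. Choosing among them after the data are seen would leave the Aim 1 comparison open to selection.

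There is a second, separate limit. Where a baseline run exists, it always precedes the stimulated run. Without a comparator, stimulation status is then aligned with run order, and so with elapsed time, fatigue and practice. Section 13.0 itself names fatigue as the main risk of the task.

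**Working it through.** **1. Which run schedules comply, and what each one estimates.** Taking two runs as the limit in Section 3.0:

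| Runs done | Unstimulated task baseline? | Contrast available |
|---|---|---|
| before + after | yes | the one in the Aim 1 hypothesis |
| before + during | yes | a different one (online effect) |
| during + after | no | no change from baseline |
| one run only | at most the baseline itself | none between runs |

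All four are permitted. Under the three-run reading of Step 3 a subject could cover all three periods, but nothing requires it.

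**2. Could a baseline come from elsewhere?** The rest epoch lies within each trial, so it shares that run's stimulation state and is not a pre-stimulation reference. Aim 2 patients do not perform the task, so they cannot supply one either.

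**3. Does a fixed pair fit the plan?** Two runs at the earlier study's 3 minutes take 2 × 3 = 6 of the 20 minutes. Two runs are already allowed, so fixing their position adds no task time. The length of stimulation is not stated.

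**4. Inputs for size (Section 5.0).** Difference 0.24 log10 units, SD 0.19 (PD group: 0.06 × √10 = 0.190), intra-class correlation 0.7, 20 subjects analysed. The 0.24 is a difference between Parkinson's and essential tremor patients, not a tDCS effect. Two-sided alpha 0.05, a t-test, and all 20 subjects in Aim 1 are my assumptions.

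The plan's 91% power cannot be reproduced uniquely, because alpha, sidedness, test and number of repeats are not given. A paired reading with n = 20 gives over 99.9%. Two groups of 10 with one measure each give 76%. The point here does not rest on that figure.

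**5. Drift in a single-phase before/after test.**
- SD of change = 0.19 × √(2 × (1 − 0.7)) = 0.147.
- SE at n = 20 = 0.147/√20 = 0.033.
- The chance of significance with no tDCS effect comes from the noncentral t distribution with noncentrality drift/SE. The drift sizes are an assumed range.

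| Drift (log10 units) | Ratio of power | n = 20 | n = 10 |
|---|---|---|---|
| 0.02 | 10^0.02 = 1.05 | 9% | 7% |
| 0.05 | 10^0.05 = 1.12 | 30% | 16% |
| 0.10 | 10^0.10 = 1.26 | 82% | 48% |

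The nominal rate is 5%.

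**6. Drift in the preparation-versus-execution contrast.** This contrast is (change in preparation) − (change in execution). If both phases drift by the same amount d, it contains d − d = 0, and no bias arises. Only a difference in drift between the phases remains. If changes in the two phases are uncorrelated with equal SD (assumption), the SD of the contrast is 0.147 × √2 = 0.208 and its SE at n = 20 is 0.208/√20 = 0.047. A between-phase difference in drift of 0.02, 0.05 or 0.10 then gives 7%, 18% or 53% false significance.

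**7. Power of a parallel sham comparison of changes (two-sample t).**

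| Test | Effect | 10 vs 10 | 5 vs 5 |
|---|---|---|---|
| Single-phase change, SD 0.147 | 0.24 | 93% | 62% |
| Preparation minus execution, SD 0.208 | 0.24 | 68% | 36% |

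For comparison, the paired preparation-versus-execution contrast in all 20 stimulated subjects has 99.8% power at 0.24, and 90% with 10 subjects.

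**The case against.** The best defence is that this is a small mechanistic study, that its hypothesis compares two phases within the same runs, and that drift common to both phases drops out. This stands: it would be wrong to say that any drift between runs is credited to tDCS. It does not remove the need for a pre-stimulation run, because each phase's change still needs a baseline. It also does not cover single-phase comparisons, which Step 3's separate analysis of each phase leaves open.

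A second defence is that the text is only ambiguous. Step 3 may intend three runs, one in each period, and nothing forbids switching the current on part-way through a run. That is fair, but a schedule that is merely possible does not secure a baseline in every subject.

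Third, there are mitigations: practice trials before surgery, an instruction to move at natural speed, one minute of rest on request, and withdrawal on further fatigue. They reduce practice and fatigue effects. They do not exclude them, and no criterion for stable performance is set.

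A reader might infer that a randomised sham arm is mandatory and comfortably powered. The documents do not support that. The 93% belongs to a single-phase change of 0.24; the Aim 1 contrast has 68% at the same effect with 10 versus 10. The 20 analysed subjects cover both aims, and the Aim 1 share is not stated. Sham subjects would also still have the research subdural electrode inserted, and the plan does not say whether the device offers a sham mode.

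A reader might also infer a definite loss of power from missing baselines. The plan gives no basis for how many subjects would lack one, so that loss cannot be sized.

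**Conclusion.** The concern holds as a gap in the Aim 1 schedule. No pre-stimulation run is required, no common timing is set, and the run limits can be read as two or three. The consequence is that some compliant subjects may add nothing to the Aim 1 contrast and others may answer a different question. This follows from the text alone and needs no numerical assumption.

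The absence of a sham limits what may be concluded. It does not make the design invalid. A single-phase before/after change cannot be separated from time, fatigue or practice: false significance is 9% to 82% for drift of 0.02 to 0.10, given SD of change 0.147, n = 20 and two-sided alpha 0.05. The preparation-versus-execution contrast is exposed only to drift that differs between the phases. The stronger reading, that no tDCS effect can be separated from time under any analysis, goes beyond the documents. The drift sizes and the Aim 1 count of 20 are assumptions.

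**What to change.** 1. Require every Aim 1 subject to complete one task run before stimulation and one at the same stated point after it, in line with the hypothesis.
2. Name the paired change between these two runs, preparation versus execution, as the single Aim 1 analysis. Treat any run during stimulation and any single-phase comparison as secondary.
3. Reconcile the run limits in Section 3.0 (Procedure steps), Section 9.0 (Step 3) and Section 13.0 (Behavioral task). The required pair needs only two runs, so it works under either reading.
4. State the planned number of Aim 1 subjects, and state as a limitation that stimulation always follows the baseline run, so a single-phase change will be reported as a change over a session that included tDCS.

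The first three items are wording. Their cost is less flexibility in the operating room, and a subject who misses either run leaves the paired analysis.

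A sham arm, or sham and active runs in randomised order within subject, is for the sponsor to weigh. The parallel form costs power on the Aim 1 contrast (68% at 0.24 with 10 versus 10, less with fewer Aim 1 subjects). The within-subject form depends on whether carry-over can be handled.

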### **Device use**

The tDCS electrodes (Soterix Medical, NY, NY, model #s 2001tE and 4x1-C3A) will be used for their intended purpose – non-invasive electrical stimulation of the brain – however, according to the manufacturer's website this is strictly an investigative tool and will be used for research purposes only.

The sECoG electrode (Ad-Tech Medical Instrument Corporation, Racine, WI, model# MS06R-IP10X-0JH) is an FDA-approved, commercially available device for intraoperative monitoring. According to the manufacturer's website, these electrodes are 'ideal for brain mapping and intraoperative monitoring of the cortical surface'. The electrode as used for intraoperative monitoring does not specify a clinical indication/population, thus, the electrodes as implemented in this protocol will be used for their intended and marketed purpose.

## **4.0 Inclusion and Exclusion Criteria/ Study Population**

Only patients considered an acceptable surgical candidate for DBS will be eligible for recruitment into this study. All diagnostic procedures, including imaging, will have taken place prior to recruitment as part of the routine diagnosis and care of movement disorder patients. In addition, patients are screened for cognitive impairment by a neuropsychologist to rule out those unlikely to benefit from DBS surgery due to cognitive impairment. No patient will receive a CT or MRI scan in order to be included in this study, and patients who did not have a CT or MRI as part of their clinical assessment will not be eligible for this study. Patient eligibility for this study will be based on the following inclusion/exclusion criteria:

### **Inclusion criteria:**

- Patients consented and scheduled for DBS surgery with the PI
- Age 18-80

### **Exclusion criteria:**

- Patients unable to actively participate in the consent process physically and/or cognitively

- Presence of scalp injury or disease
- Prior intracranial surgery with the exception of deep brain stimulation surgery
- Prior brain radiotherapy
- Prior history of intracranial tumor, intracranial infection or cerebrovascular malformation
- Prior history of seizures

The rationale for these criteria are as follows: The major risks to subjects in this study consist of #1) scalp irritation from the tDCS electrodes and #2) damage to the cortical surface or surrounding structures (such as cortical bridging veins) during insertion of the sECoG electrode. The subdural space between the skull and cortical surface can be compromised by scarring from intracranial surgery (at the site of sECoG insertion), brain radiation and/or infection of the brain. Furthermore, abnormalities of cortical vasculature, such as with an intracranial tumor or cerebrovascular malformation, may impede safe insertion of the sECoG electrode. Finally, history of seizure disorder may indicate underlying cortical abnormalities that might confound our data analysis.

## 5.0 Number of Subjects

A total of 25 subjects will be enrolled. Our group performs approximately 100 DBS surgeries per year, thus we are confident we will be able to meet our recruitment goal during the period of the award. In our previous study (Rowland et al, 2015) comparing PD (n=10) and essential tremor (n=8) patients we observed an absolute difference in cortical beta ERD during movement preparation of 0.24 with a standard deviation of 0.19 (PD  $-0.31 \pm 0.06$ , ET  $-0.071 \pm 0.05$ ,  $\log_{10}(\mu V)^2/Hz$ , mean $\pm$ SE,  $p = 0.0061$ ). Based on our experience, with an observed absolute difference in cortical beta ERD of 0.24  $\log_{10}(\mu V)^2/Hz$  and an assumed standard deviation to be as observed in our preliminary data for the PD group, we estimate a sample size of 20 subjects will be sufficient to yield a power of 91% assuming a moderate intra-class correlation of 0.7. We have allowed for 5 additional subjects in the event that any subjects are withdrawn from the study and not included in the final analysis.

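### The 91% power in section 5.0 is built on a PD-versus-ET difference rather than a tDCS effect, and cannot be reproduced from the inputs given

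*Combined protocol and SAP*

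**What the plan says.** Section 5.0 plans 25 subjects, of whom 20 are to be evaluable: "We have allowed for 5 additional subjects in the event that any subjects are withdrawn from the study". The effect size comes from an earlier study "comparing PD (n=10) and essential tremor (n=8) patients we observed an absolute difference in cortical beta ERD during movement preparation of 0.24", with group means of -0.31 (PD) and -0.071 (ET). The spread is "an assumed standard deviation to be as observed in our preliminary data for the PD group", namely 0.19. The conclusion is that "we estimate a sample size of 20 subjects will be sufficient to yield a power of 91% assuming a moderate intra-class correlation of 0.7".

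Section 1.0 sets the questions. Aim 1, in awake frameless patients, hypothesises that beta and gamma power changes will be "enhanced more so during movement preparation than execution following anodal tDCS activation". Aim 2, in framed patients who are awake or under anaesthesia, asks whether tDCS modulates cortical oscillations when there is no movement. Sections 3.0 and 9.0 restrict the motor task to awake frameless patients. The 20 subjects are not divided between the aims, and no other section adds a statistical analysis that would complete the calculation.

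**The concern.** Both aims concern what tDCS does within a patient: a change with stimulation and, for Aim 1, whether that change is larger in one movement phase than another. Section 5.0 sizes the study on a contrast between two diseases, and describes no stimulation in the comparison that produced the figure. Neither aim tests PD against ET. For Aim 2 the mismatch is wider, since 0.24 was measured during movement preparation and Aim 2 involves no movement.

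This is the only quantitative argument for the size of a study in which subjects accept a subdural electrode placed for research. A reader of section 5.0 would take it that the tDCS question has 91% power. If stimulation then showed no clear effect, the result could be read as good evidence against modulation when the study had never been sized for a stimulation effect.

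**Working it through.** **Inputs from section 5.0.** Difference 0.24 (0.31 - 0.071 = 0.239); SD 0.19 (PD standard error 0.06 × √10 = 0.190, so the plan is consistent here); ICC 0.7; n = 20; power 91%.

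**Inputs not stated, and assumed here.** Two-sided 5%; noncentral t power; ICC read as the within-patient correlation; the same correlation between all conditions.

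**Attempt to reproduce 91% at 0.24**

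- *Change with tDCS, paired.* SD of the change = 0.19 × √(2 × (1 - 0.7)) = 0.147. With n = 20, power is above 99.9%. On this contrast 91% falls between 6 subjects (88.6%) and 7 (94.6%).
- *Aim 1, preparation minus execution difference in change.* SD = 0.19 × √(4 × (1 - 0.7)) = 0.208. With n = 20, power is 99.8%.
- *Two independent groups of 10, one measure each.* Noncentrality = 0.24 / (0.19 × √(2/10)) = 2.82. Power is 76.2% (t) or 80.6% (normal approximation).

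None of these is 91%. Several variants come within two points, but each needs an input that section 5.0 does not give:

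| Variant | Power |
|---|---|
| Aim 1 contrast, only 10 subjects in that aim | 89.9% |
| Two groups of 10, mean of 2 repeats, one-sided | 90.3% (t), 92.2% (normal) |
| Two groups of 10, mean of 10 repeats, two-sided, normal approximation | 91.1% |
| Two groups of 7 and 13, change scores | 90.8% |

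**What the sample size can detect.** Detectable effect = λ × SD of contrast / √n, where λ is the noncentrality that gives 91% power: 3.48 for n = 20 and 3.72 for n = 10. For example, 3.48 × 0.147 / √20 = 0.115. With ICC 0.5 the two SDs become 0.190 and 0.269.

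| Task performers | ICC | Change with tDCS | Preparation minus execution difference in change |
|---|---|---|---|
| 20 | 0.7 | 0.115 | 0.162 |
| 20 | 0.5 | 0.148 | 0.209 |
| 10 | 0.7 | 0.173 | 0.245 |
| 10 | 0.5 | 0.223 | 0.316 |

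**Sensitivity to the true effect.** The documents give no expected tDCS effect, so the values below are assumptions chosen to show the range (ICC 0.7, change with tDCS / Aim 1 contrast).

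| Assumed true effect | n = 20 | n = 10 |
|---|---|---|
| 0.24 | above 99.9% / 99.8% | 99.5% / 89.9% |
| 0.12 | 93% / 69% | 63% / 37% |
| 0.10 | 82% / 53% | 48% / 27% |
| 0.08 | 64% / 37% | 34% / 19% |

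**The case against.** The best defence is that 91% is under-specified rather than wrong. Section 1.0 assigns different patients to the two aims; if 10 of the 20 served Aim 1, the plan's own inputs give 89.9% for the Aim 1 contrast, about one point short. This stands. A reader might infer that 91% is unattainable for every contrast in the aims, or that only one particular design yields it. The documents support neither, because the inputs needed to rule out the alternatives are absent.

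A calculation using repeated measures in two groups also has some footing. The task consists of repeated trials. Allowing 3 s rest, 3 s preparation and five cycles at the 2 s limit for one or two touches, a trial lasts 16 to 26 s, so a 3-minute task holds about 7 to 11. Averaging 7 to 11 repeats in two groups of 10 gives 90.6% to 91.2% by normal approximation. Section 1.0 also mentions comparing awake with asleep patients. Still, no aim tests a group difference, and the repeats and the split are not stated.

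It is also tempting to say that the power is inflated, or that 0.24 is too large for tDCS. Neither follows. With all 20 subjects in a within-patient contrast, the stated inputs give more than 91%. And although 0.24 is 77% of the PD preparation value (0.24/0.31), the documents hold no tDCS benchmark against which to call it implausible.

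Finally, section 5.0 is open about where 0.24 comes from, and the study is mechanistic. That limits the harm, but it does not turn the figure into power for the aims.

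**Conclusion.** The point holds in two parts. First, and without any assumption: the effect size is a disease difference and the SD is a between-patient SD, so the 91% is not power for Aim 1 or Aim 2. Second, the figure cannot be reproduced from what is stated. The conventional readings give more than 99% (within-patient, n = 20) or 76% (two groups of 10, single measure), and values near 91% appear only after an unstated input is supplied.

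This does not show that the study is underpowered or that an arithmetic slip was made. It shows that power for the tDCS question is unknown. It could be very high if tDCS shifts beta by 0.24 in all 20 subjects, or below 40% for the Aim 1 contrast if the shift is 0.08, or if it is 0.12 with 10 task performers. These figures rest on two-sided 5%, an SD of 0.19, the ICC read as within-patient correlation, and equal correlation between conditions.

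**What to change.** Rewrite the sample-size paragraph of section 5.0 as follows:

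- Remove the 91% claim.
- Say that 0.24 is a PD-ET difference and is not an expected tDCS effect, and that 0.19 is a between-patient SD.
- For each aim, state the contrast, alpha and sidedness, test, number of repeats and how they are combined, and the expected number of subjects.
- Say what the ICC correlates, and show 0.5 as well as 0.7.
- For Aim 1, give the effects detectable with 91% power by number of awake frameless task performers, as in the four-row table above, with its assumptions. Do not give the 20-performer row alone: the 20 evaluable subjects cover both aims.
- For Aim 2, give the equivalent with an SD suited to recordings without movement. The documents contain none, so any value used should be labelled as an assumption.

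The cost is a rewording. No patients or procedures are added. The downside is that the stated figure becomes less favourable.
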